6.3.1.4 Grade 4 Infusion Reactions and Infusion-Related Events

- Stop the infusion and disconnect the infusion tubing from the patient;
- TO AVOID EXACERBATION OF INFUSION REACTION OR CRS: DO NOT FLUSH THE TUBING – ASPIRATE RESIDUAL DRUG FROM THE PORT LUMEN;
- Administer IV fluids, diphenhydramine IV, acetaminophen PO/IV for fever, and oxygen and bronchodilators for mild bronchospasm, as appropriate.
- Provide appropriate ventilator and circulatory support as medically indicated;
- Agents including those listed below have been described in the management of patients with severe complications of cytokine storm and/or severe immune-related adverse events, and may be required:
 - Higher doses of corticosteroids and/or
 - Tocilizumab (anti-IL-6 receptor):
 - <30 kg: 12 mg/kg IV
 - ≥ 30 kg: 8 mg/kg [max 800 mg] IV, and/or
 - Etanercept (anti-TNF α) 0.8 mg/kg (max: 50 mg/dose) subQ
- Notify the Sponsor's Medical Monitor immediately;
- Report the event as an SAE. Patients who have a Grade 4 CRS should not receive further flotetuzumab.

THIS PROTOCOL IS FOR RESEARCH PURPOSES ONLY, SEE PAGE 1 FOR USAGE POLICY

6.3.1.5 Grade 5 Infusion Reactions and Infusion-Related Events:

- Notify the Sponsor's Medical Monitor or designee immediately;
- Report the event as an SAE.

6.4 Dose Modifications for Capillary Leak Syndrome

Risk of capillary leak syndrome (CLS) has been associated with various immunotherapies, including antibody-drug conjugates, T cell-engaging bispecific antibodies, and chimeric antigen receptor T cells. While CLS has not been observed with frequency in patients treated with flotetuzumab, rapid weight gain, decreased albumin, and systemic edema have been reported in some patients. All episodes have occurred during the multi-step lead-in dosing period and have occurred concomitantly with symptoms and signs of cytokine release syndrome (CRS).

Patients should be monitored closely for the development of CLS during flotetuzumab infusion with specific attention during the lead-in dosing period and/or during CRS occurrence. Early signs and symptoms of CLS include weight gain, new onset or worsening edema, hypotension, and decreased serum albumin. Daily weights and strict 'ins and outs' (I/Os) are strongly recommended during the dose escalation period (Cycle 1/Days 1-7 and beyond as clinically indicated). Medications and supportive measures for the treatment of such reactions should be available for immediate use, including diuretics, corticosteroids, IV fluids, vasopressors, and supplemental oxygen.

CLS Management

The following are suggested treatment guidelines for CLS related to flotetuzumab, which may be modified as needed by treating physicians/investigators according to the best practices of medicine. Early intervention is recommended at the first clinical signs of CLS in the absence of clear alternative etiologies.

6.4.1 Weight gain

For any weight gain $\geq 5\%$ from the previous treatment day, consider albumin 0.5 – 1 g/kg/dose (maximum dose 25 g) until body weight increase has resolved. If patient is normotensive or hypertensive, consider furosemide 1 mg/kg IV. For weight gain unresponsive to fluid management, consider administration of dexamethasone 5-10 mg/m²/dose (max single dose 10 mg) IV/PO or equivalent corticosteroid (e.g. methylprednisolone 1 mg/kg/dose IV). Interruption of flotetuzumab infusion may also be considered.

6.4.2 Hypotension

Hypotension can be a sign of CLS and/or CRS. If a patient is noted to be hypotensive, his or her fluid status should be managed as clinically indicated with intravenous fluids and vasopressors. Albumin or other colloids should be considered for patients whose perfusion is not restored by crystalloid alone. For hypotension unresponsive to fluid management, dexamethasone 5-10 mg/m²/dose (max single dose 10 mg) IV/PO or equivalent corticosteroid (e.g. methylprednisolone 1 mg/kg/dose IV) should be given. Interruption of flotetuzumab dosing should also be considered, particularly in patients with severe hypotension requiring vasopressor medication support. Please also see CRS management guidelines in Section 6.3.1.

THIS PROTOCOL IS FOR RESEARCH PURPOSES ONLY, SEE PAGE 1 FOR USAGE POLICY

6.4.3 Hypoalbuminemia

For any decrease in albumin ≥ 0.5 g/dL below baseline level at the start of the cycle, consider administration of albumin 0.5 – 1 g/kg/dose (maximum dose 25 g); may be repeated up to 3 times daily based on the patient's clinical status.

7.0 SUPPORTIVE CARE AND OTHER CONCOMITANT THERAPY

7.1 Concurrent Anticancer Therapy

Concurrent cancer therapy, including chemotherapy, radiation therapy, immunotherapy, or biologic therapy may NOT be administered to patients receiving study drug. If these treatments are administered the patient will be removed from protocol therapy.

7.2 Investigational Agents

No other investigational agents may be given while the patient is on study.

7.3 Supportive Care

Appropriate antibiotics, blood products, antiemetics, fluids, electrolytes, and general supportive care are to be used as necessary. Patients should receive adequate hydration during study therapy, and the addition of IV fluids to maintain intravascular volume is recommended for at least 48 hours after the start of therapy. Patients should receive appropriate *Pneumocystis jiroveci* pneumonia prophylaxis (e.g., trimethoprim-sulfamethoxazole) during study participation. Empiric anti-fungal (e.g., caspofungin, fluconazole) and antibiotic prophylaxis (e.g., levofloxacin) when ANC < 200 is strongly encouraged.

See COG Supportive Care Guidelines at <https://childrensoncologygroup.org/index.php/cog-supportive-care-guidelines>. See [Section 7.5](#) for drugs that should not be used concomitantly due to potential interactions with flotetuzumab. See below for recommendations on management of specific toxicities associated with flotetuzumab.

7.4 Growth Factors

Growth factors that support platelet or white cell number or function can only be administered in accordance with [Section 6.1.2](#) or for culture proven bacteremia or invasive fungal infection. The Study Chair should be notified before growth factors are initiated.

7.5 Concomitant Medications

Because flotetuzumab employs a mechanism of action dependent upon the engagement of T lymphocytes, the use of corticosteroids other than those employed for premedication should be limited. Chronic doses of corticosteroids in excess of 0.25 mg/kg (max 10 mg) daily of prednisone or equivalent are prohibited other than for the management of drug-related adverse experiences. Corticosteroid pretreatment should follow the recommended dose and schedule (see [Section 5.1](#)).

Vaccinations (with the exception of the annual inactivated influenza vaccine) are prohibited during the study.

8.0 EVALUATIONS/MATERIAL AND DATA TO BE ACCESSIONED

8.1 Required Clinical, Laboratory and Disease Evaluation

All clinical and laboratory studies to determine eligibility must be performed within 7 days

THIS PROTOCOL IS FOR RESEARCH PURPOSES ONLY, SEE PAGE 1 FOR USAGE POLICY

prior to enrollment unless otherwise indicated. Laboratory values used to assess eligibility (see [Section 4.0](#)) must be no older than seven (7) days at the start of therapy. Laboratory tests need **not** be repeated if therapy starts **within** seven (7) days of obtaining labs to assess eligibility. If a post-enrollment lab value is outside the limits of eligibility, or laboratory values are older than 7 days, then the following laboratory evaluations must be re-checked within 48 hours prior to initiating therapy: CBC with differential, bilirubin, ALT (SGPT) and serum creatinine. If the recheck is outside the limits of eligibility, the patient may not receive protocol therapy and will be considered off protocol therapy. Imaging studies, bone marrow aspirate, and biopsy must be obtained within 14 days prior to start of protocol therapy (repeat the imaging if necessary).

STUDIES TO BE OBTAINED	Pre-Study	During Cycle 1	Prior to Subsequent Cycles [^]
History	X	Weekly	X
Physical exam with vital signs	X	Weekly	X
Height, weight, BSA	X		X
Performance status	X		
CBC, differential, platelets	X	Twice Weekly (every 3 to 4 days) ³	Weekly ⁴
Pharmacokinetics		X ¹	X ¹
Anti-drug antibody (ADA)		X ¹⁰	X ¹⁰
Urinalysis	X		
Electrolytes including Ca ⁺⁺	X	Twice weekly (every 3 to 4 days) during Week 1, then weekly	X
Creatinine, ALT, bilirubin, AST	X	Weekly	X
Albumin	X		X
Imaging (CT or MRI) of chloroma (if clinically indicated)	X	End of Cycle 1 (if present at baseline)	End of each cycle (if present on previous study)
Bone marrow aspiration	X ^{5, 6, 12, 13}	End of Cycle 1 ⁵	End of every cycle
Pregnancy test ²	X		
ECHO or gated radionuclide study	X		X
EKG	X		X
Neurologic exam	X		X
Next-generation sequencing (NGS) MRD analysis	With bone marrow evaluation ^{7,13}	With bone marrow evaluation ⁷	With bone marrow evaluation ⁷
Peripheral T cell quantification		X ⁸	X ⁸
Cytokine analysis		X ⁹	X ⁹
Tumor Microenvironment Profiling	X ^{11, 13}		
Flow cytometry with minimal residual disease determination (MRD) ¹⁴		With bone marrow evaluation	With bone marrow evaluation

[^] Studies may be obtained within 72 hours prior to the start of the subsequent cycle.

¹ PK samples will be collected from all patients during Cycle 1. The PK sampling schedule during Cycle 1 will differ depending on dose level assignment of the patient. See [Section 8.2](#) for details. Blood samples will also be collected 30 minutes, 1 hour, 2 hours, 4 hours, 8 hours, and 24 hours after the end of infusion

on the patient's last day of protocol therapy.

- 2 Women of childbearing potential require a negative pregnancy test prior to starting treatment; sexually active patients must use an acceptable method of birth control. Abstinence is an acceptable method of birth control.
- 3 If patients have Grade 4 neutropenia then CBCs should be checked at least every other day until recovery to Grade 3 or until meeting the criteria for dose limiting toxicity.
- 4 If patients develop Grade 4 neutropenia then CBCs should be checked every 3 to 4 days until recovery to Grade 3.
- 5 Bone marrow aspirate and clot section/biopsy.
- 6 In consenting patients, CD123 site density analysis to be sent to Hematology at baseline (see [Section 8.4](#)).
- 7 In consenting patients only. See [Section 8.5](#) for details.
- 8 In consenting patients, blood samples will be collected on Cycle 1 Days 1, 8, 14, 22, and 29 and on Day 1 of subsequent cycles prior to infusion. See [Section 8.6](#) for details.
- 9 In consenting patients, blood samples will be collected on Cycle 1, Day 1 (pre-infusion) and on Cycle 1, Day 8. Additionally, if patients experience IRR/CRS, blood samples will be collected from consenting patients at the time of IRR/CRS and at the time of IRR/CRS resolution. See [Section 8.7](#) for details.
- 10 ADA samples will be collected from all patients on Cycle 1, Day 1 (pre-infusion), Cycle 3, Day 1 (pre-infusion), Cycle 5, Day 1 (pre-infusion). See [Section 8.3](#) for details.
- 11 In consenting patients, extra bone marrow aspirate will be obtained from the mandatory bone marrow biopsy prior to Cycle 1. See [Section 8.8](#) for details.
- 12 Cytogenetics and FISH will be performed on the collected bone marrow aspirate (it is recommended that cytogenetics/FISH be performed by a COG-approved laboratory).
- 13 When possible, additional aliquots of bone marrow should be collected at the time of the screening bone marrow for optional central evaluations. The preferred specimen source is bone marrow, but if additional bone marrow cannot be obtained, peripheral blood may be sent in those patients who have an absolute blast count of at least 1,000/ μ l (2 mL of peripheral blood may be submitted for each 1 mL of required marrow). Alternatively, frozen aliquots in those patients previously enrolled on APEC can be utilized if permission is granted. See [Section 8.4](#), [Section 8.5](#), and [Section 8.8](#) for details.
- 14 Analyses to be performed at Hematology. Ship samples to the address listed in [Section 8.4.5](#).

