5.0 TREATMENT PROGRAM

5.1 Overview of Treatment Plan

A cycle of therapy is 29 days. Following the end of flotetuzumab infusion on Day 29, patients will be allowed a treatment free interval of up to 3 days to allow respite. The duration of this treatment free interval will be up to the treating physician's discretion. Keeping interruptions to \leq 3 days will reduce the chance of disease rebound and lower the risk for recurrent CRS based upon clinical experience in flotetuzumab-treated adult patients. Alternatively, the treating physician may opt to skip the treatment-free interval and allow the patient to proceed immediately to the next cycle without respite, as long as the patient is experiencing clinical benefit. Clinical benefit may be defined as a reduction in leukemia related symptoms, and/or a reduction in transfusion frequency and/or a reduction or clearance of peripheral blasts. Patients with at least a PR following Cycle 2 may continue on subsequent cycles of flotetuzumab for a total of up to 6 cycles, lasting approximately 6 months. Patients should discontinue protocol therapy if they have not achieved at least a PR following Cycle 2.

During the dose escalation portion of the study, flotetuzumab will be administered by continuous intravenous infusion for a total of 28 days (NOTE: infusion ends on Day 29).

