All doses of flotetuzumab in this study are described as nanograms/kg/day. However, the drug labels are expressed in milligrams/mL. Step-up dosing will be used in the first 7 days of Cycle 1 to minimize IRR/CRS, followed by 21 days at the adult recommended phase 2 dose (RP2D) (500 nanograms/kg/day, Dose Level 1 [DL1]). If DL1 is deemed safe and tolerable based on standard immunotherapy DLT assessments ([Section 5.5](#)), an additional cohort of patients will dose-escalate to flotetuzumab at 700 nanograms/kg/day (DL2). Step-up dosing will occur during the first 8 days of Cycle 1 for this cohort. If fewer than 2 DLTs occur at DL2, this will be considered the RP2D. If there are ≥ 2 DLTs at DL2, DL1 will be considered the MTD. If DL1 is not tolerable, dose de-escalation will occur to 300 nanograms/kg/day (DL-1) with initial step-up dosing during the first 8 days of Cycle 1 for this cohort. If DL-1 is deemed tolerable, this dosing will be the MTD. Further dose de-escalation will not be permitted and will limit further exploration of flotetuzumab in this patient population. No planned step-up dosing will occur during subsequent cycles unless there is an infusion interruption of more than 3 days between cycles of flotetuzumab. If an interruption lasts > 3 days, subsequent cycle dosing should be discussed with the study chair.

Bone marrow evaluation will be performed on Day 29 (+/- 1 day) to evaluate response.

Drug doses should be adjusted based on the patient's weight measured within 7 days prior to the beginning of each cycle. Flotetuzumab continuous infusion must be administered through an IV line with a low protein binding polyethersulfone (PES) 0.2 micron in-line filter. Due to the risk of CRS, sites should have sufficient supply of tocilizumab (enough to treat a 70 kg patient x three 8 mg/kg doses) at all times for each patient on therapy. Patients will remain hospitalized for the duration of Cycle 1 for safety monitoring. Patients may receive subsequent cycles as an outpatient if the drug can be accurately and safely delivered (see [Appendix XIV](#)), and at the discretion of the treating physician and after discussion with the study chair.

Patients should receive a single dose of IT cytarabine prior to the start of Cycle 1 between Days -6 to 0. Patients may receive IT cytarabine on Day 1 of subsequent cycles or with bone marrow evaluations at the discretion of the treating physician.

IT Cytarabine Age-based dosing:

Age (yrs)	Dose
< 1	20 mg

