Flotetuzumab 500 nanograms/kg/day							X				
Flotetuzumab 600 nanograms/kg/day								X			
Flotetuzumab 700 nanograms/kg/day									X	X	

*can be given between Days -6 and 0

All Cohorts, Cycles 2+

	Day 1	Day 2-28	29
IT cytarabine*	X		End of flotetuzumab infusion
Flotetuzumab at Cycle 1 target dose	X	X	

*Patients may receive an optional dose of IT cytarabine during subsequent cycles on Day 1 or with bone marrow evaluations at the discretion of the treating physician.

If a treatment-free interval > 3 days occurs between any 2 cycles, the subsequent cycle will require step-up dosing. If a treatment-free interval > 3 days occurs between any 2 cycles, the Study Chair must be notified and the subsequent cycle dosing schedule must be discussed.

IT Cytarabine Age-based dosing:

Age (yrs)	Dose
< 1	20 mg
1-1.99	30 mg

THIS PROTOCOL IS FOR RESEARCH PURPOSES ONLY, SEE PAGE 1 FOR USAGE POLICY

2-2.99	50 mg
≥ 3	70 mg

Infusion Related Reaction/Cytokine Release Syndrome Prophylaxis prior to each subsequent cycle and for prolonged interruptions:

Prophylaxis is required prior to subsequent cycles if the treatment-free interval is greater than 24 hours. Prophylaxis is also recommended following any interruption in cycles that last >24 hours. For interruptions in cycles that last <24 hours, prophylaxis can be given at the discretion of the treating physician.

Acetaminophen: 10 – 15 mg/kg/dose (max: 650 mg/dose) IV or PO
Day 1: 30 minutes prior to starting flotetuzumab infusion, then q4-6h prn

Diphenhydramine: 0.5 – 1 mg/kg/dose (max: 50 mg) IV or PO
Day 1: 30 minutes prior to flotetuzumab infusion, then q6-8h prn

Ranitidine: 1 mg/kg/dose IV (max single dose: 50 mg) or 2 mg/kg/dose PO (max single dose: 150 mg); or equivalently dosed H2 receptor antagonist (e.g., famotidine)
Day 1: 30 minutes prior to starting flotetuzumab infusion, then q8h (IV) or q12h (PO) prn

Dexamethasone

Day 1: 5 mg/m²/dose (max single dose: 5 mg) IV or PO once 30 minutes prior to starting flotetuzumab infusion, then 5 mg/m²/dose (max single dose: 5 mg) IV or PO given 12 hours later (total daily dose: 10 mg/m²)

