5.2 Criteria for Starting Subsequent Cycles

A cycle may be repeated every 29 days, with an optional ≤ 3 day respite period between each cycle. The optional ≤ 3 day respite period will be up to the treating physician's discretion. If a patient has progressive disease at any time point or is unable to achieve a PR following Cycle 2, subsequent protocol therapy must be discontinued. Due to a risk for disease rebound and recurrent CRS, patients are allowed to proceed to subsequent cycles while awaiting disease evaluation at the discretion of the treating physician. For patients with no evidence of disease after Cycle 1, subsequent cycles should be interrupted until ANC ≥ 500 μ L and platelets $\geq 20,000/\text{mm}^3$. Patients with persistent disease are permitted to continue flotetuzumab regardless of ANC and platelet counts. Laboratory parameters as defined in the eligibility section, [Section 4.0](#), must be met, and the patient must be eligible to continue agent administration per the requirements in [Section 6.0](#).

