6.2 Dose Modifications for Non-Hematological Toxicity

- 6.2.1 Patients who have any dose-limiting non-hematological toxicity (as defined in [Section 5.5.1](#)) may continue on protocol therapy upon meeting eligibility lab requirements or baseline but should receive subsequent doses at the next lower dose level.
- 6.2.2 If a non-hematological dose-limiting toxicity recurs after one dose reduction, the patient must be removed from protocol therapy.
- 6.2.3 Patients who have a dose-limiting non-hematological toxicity that does not resolve to baseline or eligibility within 21 days after the planned start of the next treatment cycle must be removed from protocol therapy.

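### The visible schedule has one pregnancy test, before Cycle 1, although up to five more 28-day infusions may follow; repeat it before each later cycle

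*Combined protocol and SAP*

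**What the plan says.** Section 4.2.1 excludes pregnant patients because nothing is yet known about fetal or teratogenic effects in humans. It requires a test in post-menarchal girls, and it makes effective contraception a condition of participation, during therapy and for 12 weeks afterwards. Footnote 2 to the Section 8.1 table says: "Women of childbearing potential require a negative pregnancy test prior to starting treatment". In the table, the pregnancy row is marked in the pre-study column only. Appendices IV-A to IV-C (item l) place the test before Cycle 1. Appendix V (items a to r) contains none.

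Other assessments are repeated before each later cycle: history, examination, electrolytes, chemistry, albumin, cardiac imaging, EKG and neurologic examination. The table note on that column reads: "Studies may be obtained within 72 hours prior to the start of the subsequent cycle".

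On setting, Section 5.1 says of Cycle 1: "Patients will remain hospitalized for the duration of Cycle 1 for safety monitoring". Of later cycles it says: "Patients may receive subsequent cycles as an outpatient if the drug can be accurately and safely delivered", subject to the treating physician's discretion and discussion with the study chair. On timing: "Following the end of flotetuzumab infusion on Day 29, patients will be allowed a treatment free interval of up to 3 days". Patients with at least a PR after Cycle 2 may receive up to six cycles. Pregnancy is removal criterion 10.1(l), and Section 13.7.1 requires expedited reporting of a pregnancy on study or within 6 months of the last dose.

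**The concern.** Criterion 10.1(l) can act only on a pregnancy that someone has found. After Cycle 1 starts, no scheduled assessment looks for one. Testing therefore stops just before the inpatient requirement is lifted, which is when conception becomes more plausible.

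A site that follows the schedule exactly could start another 28-day infusion in a patient with an early pregnancy and no symptoms. This could happen if contraception failed in a later cycle, or if a conception shortly before entry was too early for the baseline test. What is at stake is the safety of that patient and the fetus. No estimate or decision rule of the trial depends on it.

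**Working it through.** The plan gives no figure for the interval covered by the test, so I derived it.

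**Is there only one test?** Five lists were set side by side: the 8.1 table with footnote 2, the three Cycle 1 maps (item l of each), and Appendix V. The first four all place the test before treatment or before Cycle 1, and the fifth has none. The agreement makes a broken table an unlikely explanation. Section 5.2 asks that the laboratory parameters of Section 4.0 be met before each cycle. The natural reading is the numeric limits in 4.1.8; pregnancy sits apart, as an exclusion in 4.2.1.

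**Time covered, counted from the first dose.** Inputs from Section 5.1: 28 days of infusion per cycle, a respite of 0 to 3 days, at most six cycles.
- Two cycles: 2 × 28 = 56 days, up to 56 + 3 = 59.
- Six cycles: 6 × 28 = 168 days, up to 168 + 5 × 3 = 183. This fits the plan's own approximate six months.
- After the inpatient Cycle 1 (28 days): 56 − 28 = 28 to 59 − 28 = 31 days for two cycles, and 168 − 28 = 140 to 183 − 28 = 155 days for six.

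**With a test within 72 hours before each later cycle.**
- Test to end of the uninterrupted infusion it covers: at most 3 + 28 = 31 days.
- Between successive tests in later cycles: 28 − 3 = 25 to 31 + 3 = 34 days.

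**Number of added tests.** Inputs: 20 of 47 planned patients are female (Section 11.4: 17 + 3); 27 patients are anticipated (Section 11.1). The share passing Cycle 2 is an assumption taken from the adult response rate in Section 2.3.1. That rate is printed as 26% beside 6/27, which is 22.2%, so both values are carried.
- Females: 27 × 20/47 = 11.5.
- Females with at least a PR after Cycle 2: 11.5 × 0.222 = 2.55 to 11.5 × 0.26 = 2.99.
- One test before Cycle 2 for each female and four more for each responder: 11.5 + 4 × 2.55 = 21.7, up to 11.5 + 4 × 2.99 = 23.4 (11.5 carried unrounded as 11.49).
- At the absolute maximum of 47 patients: 20 + 4 × 4.44 = 37.8 to 20 + 4 × 5.2 = 40.8.

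These counts treat every female as post-menarchal and as starting Cycle 2, and every responder as completing six cycles, so they lie at the upper end. If only half of the females start Cycle 2 and no responder goes further (also an assumption), the total at 27 patients is 11.5 × 0.5, or about 6. If the adult rate does not apply, the arithmetic ceiling is five tests for every female: 11.5 × 5, or about 57. That is not a realistic expectation.

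**The case against.** The strongest reply is that the risk is already guarded in layers: a negative entry test, mandatory contraception, history and examination before each later cycle, removal for pregnancy, expedited reporting, and a note in Appendix V that sites should do whatever else good care requires. Outpatient delivery also needs discussion with the study chair. This stands as a reason to call the event infrequent. It does not close the gap, because none of these safeguards schedules a test, and history and examination are weak tools for an early pregnancy.

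A second reply is that Section 5.2 already carries the eligibility requirements forward. If the sponsor intends that to include pregnancy, then 8.1 and Appendix V do not reflect it and need the same edit.

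A third is that few patients will be affected. Progression ends therapy at any time, Section 11.1 admits to Cycle 2 only patients with at least stable disease, and those in remission may leave for transplant. This stands too. It makes the 168-to-183-day figure relevant only to a minority (judging by the adult response rate), and it also makes the fix cheaper.

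Finally, Section 9.1 is blacked out and consent pages were removed, so guidance on pregnancy testing there cannot be excluded. The point concerns the visible schedule, which is what sites work from.

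**Conclusion.** The point holds as a modest patient and fetal safety improvement. One test covers 56 to 59 days of therapy for two cycles. It covers 168 to 183 days for patients with at least a PR after Cycle 2 who complete six. Both ranges assume respites of 0 to 3 days. The documents give neither the post-menarchal share nor any rate of contraceptive failure, so the expected number of exposed pregnancies cannot be stated; it is likely small.

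Three stronger readings are tempting and are not supported.
- A reader might infer that the baseline test could be 12 days old at the first dose (7 days before enrollment plus 5 days to start), because the pre-treatment recheck list in Section 4.0 omits pregnancy. The same section states without exception that laboratory values used for eligibility must be no more than 7 days old when therapy starts.
- A reader might lengthen the intervals with permitted delays. Section 6.2.3 requires removal only for a dose-limiting toxicity that "does not resolve to baseline or eligibility within 21 days after the planned start of the next treatment cycle", and Section 5.1 foresees longer gaps: "If a treatment-free interval > 3 days occurs between any 2 cycles, the subsequent cycle will require step-up dosing". Those holds are drug-free, so adding them measures calendar time and not exposure. Gaps over 3 days also bring in the study chair.
- A reader might take this as a threat to the trial's results. The DLT rules, the MTD/RP2D determination and the sample size do not depend on it.

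**What to change.** Add a pregnancy test for post-menarchal patients in three places: the column for subsequent cycles in the 8.1 table, footnote 2, and the Appendix V list. Run it on the chemistry sample already drawn within 72 hours before each cycle. Require a negative result before that cycle's infusion starts, and cross-refer to 10.1(l).

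The cost is one inexpensive assay per later cycle with no extra blood draw, plus the wording changes. At 27 patients that is at most roughly 22 to 23 tests over the whole study if the adult response rate applies. Sites must have the result in hand before starting, which matters most when a patient moves to the next cycle without a respite.
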